**CONFIDENTIAL** 

Date: Version: Status: Page:

#### 2.4 Secondary endpoints

#### 2.4.1 Confirmatory secondary endpoints

Confirmatory secondary endpoints are listed in Section 4.2.2.1 in the protocol.

All confirmatory secondary endpoints, except proportion of subjects losing at least 4% of baseline body weight at week 16, are planned to be assessed at week 56 and will be analysed using the same primary MI approach as used for the primary endpoints and to address the effectiveness estimand. The statistical model for continuous confirmatory secondary endpoints will be ANCOVA with covariates listed in Table 2–4 with baseline body weight replaced by baseline measurement of endpoint to be analysed. Binary confirmatory secondary endpoints will be analysed using logistic regression in the same way as for 5% responders.

The effectiveness estimand at week 16 will be assessed using the confirmatory secondary endpoint of proportion of subjects losing at least 4% of baseline body weight at week 16. Subjects with missing values for weight at week 16 will be considered non-responders.

Sensitivity analyses will be carried out for all confirmatory secondary endpoints, except for proportion of subjects losing at least 4% of baseline body weight at week 16. See Table 2–6 for details on planned analysis methods, multiple imputation approach and sensitivity analyses.

The efficacy estimand will also be assessed for confirmatory secondary endpoints, except for proportion of subjects losing at least 4% of baseline body weight at week 16, using MMRM as described for the primary endpoints.

## 2.4.2 Description of the hierarchical testing procedure to address the effectiveness estimand for primary and confirmatory secondary endpoints

The tests of superiority of liraglutide 3.0 mg to placebo for each of the endpoints are tested in a hierarchical manner in the order in which the endpoints are presented. The two primary endpoints are included in the statistical testing hierarchy below, even though the primary objective will only be met if superiority of liraglutide 3.0 mg vs. placebo is demonstrated for each of the primary endpoints. The test hierarchy is given in Table 2–6. The first endpoints to be tested are all assessing aspects of weight loss (e.g., relative change in body weight, achieving a certain magnitude of weight loss, and change in waist circumference); these endpoints are followed by endpoints assessing change in weight-related comorbidities and/or consequences of excess body weight and 'feeling and function' indicators.

Statistical Analysis Plan		Date:	07 July 2018	Novo Nordisk
Trial ID: NN8022-4274	CONFIDENTIAL	Version:	1.0	
UTN: U1111-1177-5059	CONFIDENTIAL	Status:	Final	
EudraCT No.: 2015-005592-24		Page:	18 of 24	

## Table 2–6Hierarchical order and type of statistical method to address the effectiveness
estimands for primary and confirmatory secondary endpoints

Test order	Endpoint	Endpoint Type	Statistical model	MI approach	Sensitivity analyses #
	Primary endpoints				
1	Change in body weight (%) from baseline to week 56	Continuous	ANCOVA	Jump to reference	McEvoy wANCOVA Sacks Tipping point Unadjusted ANCOVA
2	Proportion of subjects losing at least 5% of baseline body weight at week 56	Binary	Logistic Regression	Jump to reference	McEvoy Sacks Tipping point Risk difference
	Confirmatory secondary endpoints				
3	Proportion of subjects losing more than 10% of baseline body weight at week 56	Binary	Logistic Regression	Jump to reference	McEvoy Tipping point
4	Proportion of subjects losing more than 15% of baseline body weight at week 56	Binary	Logistic Regression	Jump to reference	McEvoy Tipping point
5	Proportion of subjects losing at least 4% of baseline body weight at week 16 (addresses the effectiveness estimand for week 16)	Binary	Logistic Regression	Not needed, as subjects with missing body weight values at week 16 will be considered non-responders.	
6	Change from baseline to week 56 in waist circumference (cm)	Continuous	ANCOVA	Jump to reference	McEvoy wANCOVA Tipping point
7	Change from baseline to week 56 in Short Form-36 (SF-36) v2.0 acute physical functioning score	Continuous	ANCOVA	Jump to reference	McEvoy wANCOVA Tipping point
8	Change from baseline to week 56 in impact of Weight on Quality of Life-Lite (IWQoL-Lite for CT), physical function domain (5-items) score	Continuous	ANCOVA	Jump to reference	McEvoy wANCOVA Tipping point
9	Change in six minute walking distance test (m) from baseline to week 56	Continuous	ANCOVA	Jump to reference	McEvoy wANCOVA Tipping point

MI Multiple Imputation;

# See Table 2–5.

#### 2.4.3 Supportive secondary endpoints

#### 2.4.3.1 Efficacy endpoints

Supportive secondary efficacy endpoints addressing the secondary efficacy objectives are listed in Section 4.2.2.2 in the protocol. The questionnaire for Weight related sign and symptom (WRSS)

Statistical Analysis Plan		Date:	07 July 2018	Novo Nordisk
Trial ID: NN8022-4274	CONFIDENTIAL	Version:	1.0	
UTN: U1111-1177-5059	CONFIDENTIAL	Status:	Final	
EudraCT No.: 2015-005592-24		Page:	19 of 24	

measure will not be validated until after DBL. Therefore the total score cannot be calculated and the supportive secondary endpoint "Weight related sign and symptom (WRSS) measure, total score" will not be analysed. Instead frequencies for categorical responses will be presented for each item and by visit.

#### Secondary endpoints addressing the first of the secondary efficacy objectives

Supportive secondary endpoints will be evaluated to address the effectiveness estimand. These endpoints will be analysed using the same MI approach as used for the primary and confirmatory endpoints and to address the effectiveness estimand.

The statistical model for continuous endpoints will be ANCOVA with covariates listed in

Table 2–4 with baseline body weight replaced by baseline measurement of endpoint to be analysed. The statistical model for proportions will be analysed using logistic regression.

In addition to the supportive secondary efficacy endpoints regarding IWQoL-Lite for CT listed in the protocol, analyses and outputs for the IWQoL-Lite for CT physical domain (not to be confused with IWQoL-Lite for CT physical *function* domain) will be made.

#### Secondary endpoints addressing the second of the secondary efficacy objectives

Adherence, used both as an endpoint and as a factor for weight loss will be investigated in an exploratory manner. In addition to the adherence definitions, analyses and displays presented below, alternative definitions, analyses and displays may be made if deemed relevant. These will be described as post-hoc analyses when reporting the trial.

- Adherence to trial product is defined as at least one administration of trial product per week
- Adherence to caloric diet is defined as at least one food diary entry for five days per week
- Adherence to physical activity is defined as at least 50% of the target minutes per week
- Adherence to caloric diet and physical activity is defined as being adherent to both caloric diet and physical activity
- Adherence to trial product, caloric diet and physical activity is defined as being adherent to all three randomised trial product, caloric diet and physical activity

Number of weeks adherent to treatment will be analysed by fitting a regression model for count data (e.g. negative binomial) with factors and covariates listed in Table 2–4.

Further, the association of adherence to trial product, caloric diet and/or physical activity with relative change of body weight will be explored across the total planned treatment duration. For that purpose, the following variables will be derived: First, the total treatment period (from randomisation to end-of-treatment visit) will be divided into four periods (each e.g. 12 (visit 2 to

Statistical Analysis Plan		Date:	07 July 2018	Novo Nordisk
Trial ID: NN8022-4274	CONFIDENTIAL	Version:	1.0	
UTN: U1111-1177-5059	CONFIDENTIAL	Status:	Final	
EudraCT No.: 2015-005592-24		Page:	20 of 24	

10), 12 (visit 10 to 16), 16 (visit 16 to 20) and 16 (visit 20 to 24) weeks). Second, number of weeks adherent to trial product, caloric diet or physical activity during each of the four periods will be divided by total number of weeks of the respective period. Then, plots of relative change in body weight vs. adherence to trial product, caloric diet and/or physical activity will be created.

In addition, relative change of body weight will be summarized descriptively stratified by visits and different adherence categories, which will be defined based on the distribution of observed data.

#### Exploratory analysis of week 16 responders

In this exploratory analysis, subjects who lost  $\geq 4\%$  of their baseline body weight at week 16 after randomisation are considered as 'week 16 responders'. Subjects who lost < 4% of their baseline body weight at week 16 after randomisation are considered as 'week 16 non-responders'. Hence, four 'week 16 response' groups can be defined:

- 1.  $\geq$ 4% weight loss at 16 weeks (liraglutide 3.0 mg)
- 2. <4% weight loss at 16 weeks (liraglutide 3.0 mg)
- 3.  $\geq$ 4% weight loss at 16 weeks (placebo)
- 4. <4% weight loss at 16 weeks (placebo)

The change in body weight (%) from baseline to week 56 will be explored among the four 'week 16 response' groups based on descriptive statistics only. Since the comparisons of the four 'week 16 response' groups are influenced by post-randomisation factors, no formal testing will be done.

#### 2.4.3.2 Safety endpoints

Descriptive statistics for all safety endpoints will be provided with the aim to compare liraglutide 3.0 mg and placebo. All analyses and tabulations will be done using the safety analysis set. Unless otherwise stated, no formal statistical analyses are planned for the safety endpoints.

#### **Adverse events**

AEs will be coded using the current version of Medical Dictionary for Regulatory Activities (MedDRA). All AEs will be presented based on system organ class, high level group term and preferred terms.

Adverse events will be classified and analysed as 'in trial' and 'on drug' defined in terms of patient years of observation (PYO) and patient years of exposure (PYE), respectively. For each subject, PYO is defined as number of days from date of randomisation until and including date of follow-up visit or date of last contact. For each subject PYE is defined as time intervals of exposure to trial drug including an ascertainment window of 14 days for each exposure interval.

AEs, which occurred while the subject was in trial or on drug will be summarised descriptively, whereas AEs, which occurred before first exposure to trial drug or after the follow-up visit will only

Statistical Analysis Plan		Date:	07 July 2018	Novo Nordisk
Trial ID: NN8022-4274	CONFIDENTIAL	Version:	1.0	
UTN: U1111-1177-5059	CONFIDENTIAL	Status:	Final	
EudraCT No.: 2015-005592-24		Page:	21 of 24	

be presented in listings. AEs will be displayed in terms of the number of subjects with at least one event (N), the percentage of subjects with at least one event (%), the number of events (E) and the event rate per 100 years (R). Furthermore, AEs will be summarised by seriousness, severity, relation to trial drug, premature treatment discontinuation due to AE and outcome.

Summary tables by system organ class, high level group term and preferred term will be made for all AEs, SAEs, AEs possibly or probably related to trial drug, severe AEs, AEs occurring in at least 5% of the subjects in any arm, and AEs occurring in at least 1% of the subjects in any treatment arm.

AEs requiring completion of specific event forms will be presented in tables and listings. In addition, time to occurrence of these AEs will be presented in cumulative incidence plots.

#### **Physical examination**

Outcome of the physical examination at screening and change in the physical examination category at week 56 will be summarised in tables.

#### Pulse

Pulse (beats/min) at baseline and change of pulse at week 56, will be summarised in tables by week and treatment. Additionally, categories based on the maximum change from baseline until week 56 (>0, >5, >10, >20 beats/min) and categories based on the maximum value until week 56 (>80, >90, >100 beats/min) will be included in summary tables. Additionally, change in pulse from baseline to week 56 will be evaluated in the trial observation period similar to the primary analysis for the primary estimand but using the safety analysis set.

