#### Taxonomy of week 56 assessments being available or missing

A given assessment at week 56 may be available or missing and Table 2–1 defines the taxonomy for this. Note this is done per assessment not per subject, as subjects may belong to different types for different assessments (a subject may have "available on treatment (AT)" for weight but "missing on treatment (MT)" for waist circumference).

Statistical Analysis PlanDate:07 July 2018NovoTrial ID: NN8022-4274CONFIDENTIALVersion:1.0UTN: U1111-1177-5059Status:FinalEudraCT No.: 2015-005592-24Page:8 of 24	07 July 2018 Novo Nordisk 1.0 Final 8 of 24
---	--

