#### Table 2–1Taxonomy of week 56 assessments being available or missing

Assessment at week 56	On drug at week 56	Type description	Type Abbreviation
Available	Yes	Available on randomised treatment: Subjects who did not discontinue randomised treatment prematurely. Include those that stop and restart trial product.	AT
	No	Available drop-outs: Subjects who discontinued randomised treatment prematurely but returned to have an assessment at week 56; so-called retrieved drop-outs.	AD
Missing	Yes	Missing on randomised treatment : Subjects who did not discontinue randomised treatment prematurely. Include those that stop and restart trial product.	МТ
	No	Missing drop-outs : Subjects who discontinued randomised treatment prematurely and did not return to have an assessment at week 56; so-called non-retrieved drop-outs.	MD

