#### Primary approach for handling of missing values

The primary approach for multiple imputations of missing values of body weight at week 56 (type MT+MD) for both the liraglutide 3.0 mg and placebo group is by sampling among all available assessments at week 56 in the placebo group (type AT+AD). This approach is also known as jump to reference and makes the assumption that subjects instantly after discontinuation lose any effect of randomised treatment beyond what can be expected from placebo treatment as adjunct to diet and exercise. Body weight measurements at visits between baseline and week 56 are not used for this imputation approach. The multiple imputation approach is done in three steps.

- **Imputation**: Step 1 defines an imputation model based on placebo subjects, which is used to impute missing body weight values at week 56 in both arms. This will be done 100 times and results in 100 complete data sets. A more detailed explanation of this step is given below.
- Analysis: Step 2 analyses each of the 100 complete data sets, using the statistical model defined in Section 2.3.1.1 and 2.3.1.2 and saves the 100 estimation results.

• **Pooling**: Step 3 integrates the 100 estimation results into a final result using Rubin's formula. The imputation model in step 1, uses placebo subjects from FAS with non-missing body weight measurements at baseline and week 56. The imputation model is a linear regression of body weight

Statistical Analysis Plan Trial ID: NN8022-4274 UTN: U1111-1177-5059 EudraCT No.: 2015-005592-24	CONFIDENTIAL	Date: Version: Status: Page:	07 July 2018 1.0 Final 13 of 24	Novo Nordisk
---	--------------	---------------------------------------	--	--------------

(kg) at week 56 on the factors and covariates listed in Table 2–4 (except randomised treatment) with no interactions. The estimated posterior distribution for the parameters (regression coefficients and variances) in the imputation model is then used to impute missing week 56 body weight values for both randomised treatment arms.

If 100 copies are not sufficient to establish stable results, a higher number will be used. The multiple imputations will be generated using Novo Nordisk trial number 80224274 as seed number.

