#### Sensitivity analyses of the primary endpoints for the effectiveness estimand

The sensitivity analyses will address the robustness of the primary approach for handling of missing values. In particular the sensitivity analyses address how assumptions on how body weight progresses after discontinuation of randomised treatment impact the estimated treatment difference between liraglutide 3.0 mg and placebo. The sensitivity analyses include the following.

- A multiple imputation approach as described by McEvoy where missing body weight measurement at week 56 for non-retrieved drop-outs (type MD) are imputed by sampling from values obtained from retrieved drop-outs (type AD) in each randomised treatment arm and according to the timing (monthly) of last available observation (of body weight) on randomised treatment (LAO-OT). Missing body weight measurements at week 56 for subjects on drug treatment (type MT) are imputed by sampling from type AT in the relevant randomised treatment arm. Thus, the imputation model for each randomised treatment arm and timing of LAO-OT is a linear regression of body weight (kg) at week 56 on the factors and covariates listed in Table 2–4 (except randomised treatment arm) with no interactions and LAO-OT of body weight. If timing by month is too restrictive, quarters, half-years, or excluding timing will be used.
- A weighted ANCOVA (wANCOVA) where returning drug discontinuing subjects (AD) are upweighted relative to their proportion of all drug discontinuing subjects (AD+MD) to account for the subjects not returning for assessments at week 56. Similarly, AT subjects are up-weighted relative to their proportion of all drug continuing subjects (AT+MT). The up-weighing is done by randomised treatment arm and the timing of LAO-OT. Subjects who are missing the weight measurement at week 56 (MD+MT) are assigned a weight of 0 (zero).

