- A single imputation approach as done by Sacks. Missing weight measurement at week 56 for subjects who drop-out (type MD) are imputed using a weight regain rate of 0.3 kg/month after last available observation (LAO) of body weight. Change from baseline is truncated whenever the extrapolation would lead to a positive weight gain relative to baseline. LAO does not need to be the same as LAO-OT as subjects are allowed to come to scheduled visits after discontinuing randomised treatment. When a subject's LAO represents a gain in weight relative to baseline, no additional gain will be imputed, and the unfavourable gain is carried forward to week 56. Missing weight measurement at week 56 for subjects on treatment (type MT) will be imputed using the LAO. The weight regain imputation will be done for both randomised treatment arms.

Statistical Analysis Plan Trial ID: NN8022-4274 UTN: U1111-1177-5059 EudraCT No.: 2015-005592-24	CONFIDENTIAL	Date: Version: Status: Page:	07 July 2018 1.0 Final 14 of 24	Novo Nordisk
UTN: U1111-1177-5059 EudraCT No.: 2015-005592-24	CONFIDENTIAL	Status: Page:	Final 14 of 24	

Additionally, a version where only the liraglutide 3.0 mg arm uses the regain rate while the placebo arm uses LAO (corresponding to a weight regain rate of 0 kg/month) will be performed.

• Tipping point analysis. In a similar manner as above for a range of weight regain rates (starting from 0.1 kg/month and in intervals of 0.1 kg/month) for MD in liraglutide 3.0 mg arm will be used to define a tipping point in which superiority of liraglutide 3.0 mg disappears. In this analysis, the placebo arm will be imputed by LAO.

Figure 2–1 and Table 2–5 give an overview of the handling of missing values at week 56 assessments.

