### Figure 2–1 Illustration of imputation approaches for the effectiveness estimand

Jump to refere	nce (multiple imputation)
Liraglutide	AT+AD 7 MT+MD
Placebo	AT+AD MT+MD
McEvoy (multip	ole imputation)
Liraglutide	$ \begin{array}{c} AT \\ AD \end{array} \longrightarrow \begin{array}{c} MT \\ MD \end{array} $
Placebo	$ \begin{array}{c} AT \\ \hline AD \end{array} \longrightarrow \begin{array}{c} MT \\ \hline MD \end{array} $
McEvoy is done by	timing (e.g. monthly) of randomised treatment discontinuation
Sacks (single in	iputation)
Liraglutide	ATLAO $\rightarrow$ MTADLAO + 0.3 $\rightarrow$ MD
Placebo	$ \begin{array}{ c c c c c c c c c c c c c c c c c c c$
LAO: Last available	observation irrespective of whether on randomised treatment or not
An arrow indicates $AT = A$ MT = M AD = A MD = M	from which group an imputation is done vailable on randomised treatment lissing on randomised treatment vailable drop-out lissing drop-out

Statistical Analysis Plan Trial ID: NN8022-4274 UTN: U1111-1177-5059 EvdreCT No.: 2015 005502 24	CONFIDENTIAL	Date: Version: Status:	07 July 2018 1.0 Final	Novo Nordisk
EudraCT No.: 2015-005592-24		Page:	16 of 24	

Approach	Description	Assumptions
Jump to reference (multiple imputation)	Liraglutide and placebo MT+MD imputed from placebo AT+AD (i.e., all available placebo assessments at week 56)	
 
Liraglutide MD lose any treatment effect instantly after drop-out
 
Placebo AT and placebo AD are assumed to have the same weight loss
 

McEvoy (multiple imputation)	Separately for the two randomised treatment arms: MD imputed from AD by matching on time (month) of drop-out MT imputed from AT	
 
AD is representative of the MD for each randomised treatment arm
 
AT is representative of the MT for each randomised treatment arm
 

Weighted ANCOVA (wANCOVA)	No imputation. Separately for the two randomised treatment arms: AD subjects are up-weighted relative to their proportion of AD+MD and timing of drop- out AT subjects are up-weighted relative to their proportion of AT+MT	
 
AD is representative of the MD for each randomised treatment arm
 
AT is representative of the MT for each randomised treatment arm
 

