#### Amylase and lipase

Shifts from baseline to highest value in trial period to UNL, 2xUNL and 3xUNL will be summarised in tables.

Mean plots, geometric mean plots and box plots by gender, visit and treatment will be prepared. Change from week 0 to week 56 will also be presented by empirical distribution plots.

Number and percentage of subjects with amylase and lipase levels  $\geq$ UNL,  $\geq$ 2xUNL or  $\geq$ 3xUNL will be tabulated by week and treatment. Subjects with values  $\geq$ 2xUNL will additionally be presented with spaghetti plots.

Additionally, change in amylase and lipase from baseline to week 56 will be evaluated in the in trial observation period similar to the primary analysis for the primary estimand but using the safety analysis set.

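### The modelled comparisons of pulse, amylase and lipase impute from placebo those liraglutide subjects who are still on drug but lack a week 56 value; for pulse this is a small bias towards no difference, removable in one sentence

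*SAP*

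**What the plan says.** SAP 2.4.3.2 keeps safety mainly descriptive but adds a modelled comparison for three measures. For pulse, "change in pulse from baseline to week 56 will be evaluated in the trial observation period similar to the primary analysis". For amylase and lipase the change is likewise to be assessed in the in-trial period, "similar to the primary analysis for the primary estimand but using the safety analysis set". Protocol 17.4.3.2 has the same wording.

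The primary analysis has one primary imputation approach, jump to reference. SAP Table 2–5 describes it as "Liraglutide and placebo MT+MD imputed from placebo AT+AD". SAP 2.3.2.2 says that it "makes the assumption that subjects instantly after discontinuation lose any effect of randomised treatment". In the same table, the assumption listed for the liraglutide arm concerns missing drop-outs (MD) only.

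SAP Table 2–1 defines the on-treatment types, including MT (on drug, assessment missing), as "Subjects who did not discontinue randomised treatment prematurely. Include those that stop and restart trial product". The type is assigned separately for each measurement: "Note this is done per assessment not per subject, as subjects may belong to different types for different assessments". The SAP's own example is a subject with weight available on treatment and waist circumference missing on treatment.

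The sensitivity analyses for week 56 treat MT differently. In the multiple imputation from retrieved drop-outs, "subjects on drug treatment (type MT) are imputed by sampling from type AT in the relevant randomised treatment arm". In the weight-regain imputation, "Missing weight measurement at week 56 for subjects on treatment (type MT) will be imputed using the LAO", and the tipping-point analysis does the same. The weighted ANCOVA up-weights AT subjects within arm. Table 2–6 lists these analyses for the primary and confirmatory endpoints only, so none is planned for the three safety models.

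**The concern.** A liraglutide subject who is taking the drug at week 56 but has no pulse reading that day has a true week 56 pulse that reflects the drug. The planned rule replaces it with a draw from the placebo arm. The reason given for the rule is that the effect goes when treatment stops, and this subject has not stopped. The mismatch exists within the in-trial, treatment-policy question that the SAP has chosen, so it is not a preference for another estimand.

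Direction is what makes it worth raising. For weight loss, filling in placebo values works against liraglutide and is a cautious choice for a superiority claim. For an unwanted effect the same rule pulls the modelled difference towards zero. Because type is set per assessment, good retention for body weight does not ensure that few subjects are MT for pulse or for the enzymes.

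**Working it through.** **The plan's own dilution arithmetic.** The SAP gives no figure for the three safety models. SAP 2.1 does apply the same mixture logic to % weight change, with 30% of liraglutide subjects given the placebo mean: 0.7 × (−9) + 0.3 × (−4) = −7.5, so the difference is −7.5 − (−4) = −3.5. The mixture SD is √(49 + 0.3 × 0.7 × 25) = 7.37. With 141 per arm, the Satterthwaite t test then has 98.3% power. All of these agree with the SAP.

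**The same logic for pulse.** Let d be the on-drug difference from placebo, p the share of liraglutide subjects off drug at week 56 (taken as placebo-like) and m the MT share.
- In-trial difference: d × (1 − p).
- Expected under the planned rule, with MT set to placebo: d × (1 − p − m).
- Bias: −d × m, whatever the value of p.

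Inputs: d = 2-3 beats/min (protocol 18.1, heart rate increase). That section does not say that the rise is net of placebo, so treating it as such is an assumption. The documents give no MT share, so m = 2%, 5% and 10% are assumed. They give no SD for pulse change either, so 9 is assumed. The unadjusted standard error is 9 × √(2/141) = 1.07.

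| MT share | Bias, d = 2 | Bias, d = 3 | In standard errors |
|---|---|---|---|
| 2% | 0.04 | 0.06 | 0.04-0.06 |
| 5% | 0.10 | 0.15 | 0.09-0.14 |
| 10% | 0.20 | 0.30 | 0.19-0.28 |

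With an SD of 7 (standard error 0.83) or 11 (1.31), the 5% row becomes 0.12-0.18 or 0.08-0.11 standard errors. As an extreme bound, if 30% of liraglutide subjects were missing and all were MT, the bias would be 0.6-0.9 beats/min, still below one standard error at an SD of 9.

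**Simulation check.** Settings: 141 per arm, d = 2.5, SD 9, 15% MD, 10-13% retrieved drop-outs, off-drug pulse equal to placebo, 20 imputations, ANCOVA on baseline pulse, Rubin pooling, 400 trials. True in-trial difference / planned rule / MT from own-arm AT:
- 2% MT: 1.80 / 1.74 / 1.78. Gap between the two rules: 1.782 − 1.737 = 0.045, against 2.5 × 0.02 = 0.05.
- 5% MT: 1.88 / 1.76 / 1.88. Gap: 1.884 − 1.757 = 0.127, against 0.125.
- 10% MT: 1.88 / 1.59 / 1.83. Gap: 1.827 − 1.585 = 0.242, against 0.25.

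The pooled standard errors under the two rules are 1.02 and 1.02, 1.03 and 1.03, 1.05 and 1.06, so own-arm imputation costs essentially no precision.

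The simulation confirms the formula and the precision. It does not show independently that own-arm imputation would be unbiased in this trial: MT subjects were generated like AT subjects, so recovery of the true value is built in.

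**Amylase and lipase.** The algebra is the same, but the documents state no drug effect on either enzyme. Only the relative statement holds: the MT subjects' share of any effect is set to zero.

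**The case against.** The strongest objection is that this does not matter. The models are supplementary, lie outside the testing hierarchy, and no stated decision depends on them. The by-week tables, the categories of maximum pulse and maximum change, and the enzyme shift and threshold tables are not described as imputed, so a safety signal would not rest on the models alone. At MT shares of 2-5% the pulse bias is 0.04-0.15 beats/min. All of this stands, and it limits the point to a cheap improvement.

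It can also be said that a resemblance to the primary analysis does not specify the imputation. That is fair, but jump to reference is the only primary approach. If something else is meant, a sentence saying so is still needed.

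A reader might infer more than the documents support:
- **That jump to reference is wrong for drop-outs too.** Protocol 18.1 says that the heart-rate increase disappears when treatment stops, which supports the planned MD rule for pulse. Observed values of retrieved drop-outs are kept, and their dilution of the difference belongs to the in-trial effect.
- **That the enzyme models are biased towards no harm.** That presumes a rise on drug, which the documents do not state.
- **That every other missing-data rule in the SAP keeps MT subjects in their own arm.** This is true of the week 56 methods. At week 16, every subject with a missing weight counts as a non-responder.
- **That an on-treatment model is required.** The repeated-measures model of SAP 2.3.3 answers a different question and uses data only up to the first discontinuation, so it drops values after a restart although Table 2–1 counts restarters as on treatment. It is optional.

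**Conclusion.** The point holds as a minor one. On the natural reading, on-drug liraglutide subjects with a missing week 56 value receive placebo-like values in the three modelled safety comparisons, and the SAP's rationale does not extend to them. For pulse the modelled difference is pulled towards zero by the MT share times the on-drug rise: at most 0.30 beats/min, or about 0.3 standard errors, over the range considered. This rests on an assumed MT share of up to 10%, an assumed SD of 9, and the 2-3 beats/min in protocol 18.1 being the difference from placebo. It would not by itself change a conclusion, and it should not be read as the plan concealing a safety signal. For amylase and lipase the dilution is real if there is a drug effect, but neither its direction nor its size can be given.

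**What to change.** In SAP 2.4.3.2, state that in the in-trial models of pulse, amylase and lipase, MT subjects are imputed from AT subjects of their own randomised arm, following the MT rule of the first sensitivity analysis in SAP 2.3.2.2, and that MD subjects are handled as planned.

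The cost is one sentence and a rule that the SAP already defines, with no material change in the standard error. The downside is an assumption: that subjects on drug with a missing week 56 value resemble those on drug in the same arm whose value was obtained. If MT subjects differ systematically, some bias remains, in a direction that cannot be foreseen.
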